11.7 Surgery

All patients in this study will have a temporary ileostomy (diversion of the bowel into a bag) at the time of surgery unless they are having an APR, in which case they will have a permanent colostomy. This is done to decrease the risk of a leak or complication following surgery. In most cases this ileostomy is temporary, however, depending on the location of the tumor, it may be permanent.

Expected Adverse Events for Surgery

More Frequent (>10%)

- Infection of wound
- Intra-abdominal abscess
- Urinary retention
- Urinary tract infection
- Ileus
- Stoma irritation
- Pain/Rectum
- Anastomotic suture separation/leak
 - 10% in HDRBT literature
- Dehydration

Less Frequent (<1%)

- Thrombosis/Embolism
- Pneumonia
- Cardiac Ischemia/Infarction
- Fistula – rectovaginal/rectourethral/perineal
- Fecal incontinence
- Stricture at suture line

11.8 Chemotherapy

Chemotherapy is considered standard of care. Only grade 3 or greater side effects thought to be related to chemotherapy will be recorded. Since this is standard of care treatment, adjustments made to the chemotherapy regimen are left to the discretion of the treating oncologists.

The following are very common potential side effects of capecitabine (occurring in more than 50 out of 100 people):

Anemia hand-and-foot syndrome.

The following are common potential side effects of capecitabine (occurring in 20 to 50 people out of 100):

Fatigue or weakness, vomiting, abdominal pain, loss of appetite, neutropenia, risk of infection, mouth sores, unusual burning or tingling sensations in hands or feet.

The following are less common potential side effects associated with capecitabine (Occurring in 5 to 20 people out of 100):

Constipation, eye irritation, vision changes, or conjunctivitis, difficulty breathing, pain (including back pain, muscle pain, or joint pain), lethargy, headaches, indigestion or heartburn, dizziness, insomnia, dehydration, coughing, hair loss, taste changes and mood changes.

The following are even less common potential side effects of capecitabine (occurring in less than 5 people out of 100):

Nosebleeds, sore throat, stomach ulcers, nail problems, increased sweating, sensitivity to the sun, hot flashes, drowsiness, shakiness, weight gain, weight loss, high triglycerides, coughing, asthma, pneumonia, hypotension, hypertension, and vertigo.

Serious side effects we will be looking for very closely will be:

Depression, signs of blood clots, blood in the stool, very severe constipation, nausea, vomiting, or mouth sores, severe redness of the hands or feet, an increase in tumor size or appearance of new tumors, a fever or signs of infection, signs of liver problems and signs of allergic reaction.

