7.3.5 Capecitabine (Xeloda)

Capecitabine shall be delivered at $825\text{mg}/\text{m}^2$ BID during IMRT radiotherapy. Dose modification shall occur as follows:

- If $\text{ANC} < 1000/\text{mm}^3$ capecitabine will be held until the blood counts recover above these values and the patient can resume full dosing
- If platelet count $< 100,000/\text{mm}^3$, capecitabine will be held until the blood counts recover above these values and the patient can resume full dosing

Event Name	Hand-Foot Skin Reaction
Grade of Event	Management/Next Dose for Capecitabine
\leq Grade 1	No change in dose
Grade 2	Hold until \leq Grade 1. For the first appearance resume at 100% of the dose. For the second appearance, dose reduce to $650\text{ mg}/\text{m}^2$ For the third appearance, dose reduce to $500\text{ mg}/\text{m}^2$ For the fourth appearance, discontinue.
Grade 3	Hold until \leq Grade 1. For the first appearance, dose reduce to $650\text{ mg}/\text{m}^2$ For the second appearance, dose reduce to $500\text{ mg}/\text{m}^2$ For the third appearance, discontinue.
Grade 4	Hold until \leq Grade 1. For the first appearance, dose reduce to $500\text{ mg}/\text{m}^2$ For the second appearance, discontinue.

Event Name	Diarrhea
Grade of Event	Management/Next Dose for Capecitabine
\leq Grade 1	No change in dose
Grade 2	For the first appearance, dose reduce to $650\text{ mg}/\text{m}^2$ For the second appearance, dose reduce to $500\text{ mg}/\text{m}^2$ For the third appearance, discontinue. ¹
Grade 3	For the first appearance, dose reduce to $650\text{ mg}/\text{m}^2$ For the second appearance, dose reduce to $500\text{ mg}/\text{m}^2$ For the third appearance, discontinue. ¹

¹Capecitabine may be discontinued at the discretion of the investigator

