7.5.2 Patients receiving External Beam Radiotherapy

Diarrhea, skin irritation, fatigue, urinary tract irritation, and decreased blood counts are the main side effects experienced during concurrent chemotherapy and pelvic radiation therapy. Standard supportive care measures may be used at the treating physician's discretion throughout the course of therapy, including antidiarrheal agents (loperamide, etc.), skin creams, and phenazopyridine (Pyridium). Specific guidelines for dose-reducing capecitabine as needed are given in Section 7.3.5.

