11. ADVERSE EVENT REPORTING

11.1 General

Adverse event collection and reporting is a routine part of every clinical trial. This study will use the descriptions and grading scales found in the NCI Common Terminology Criteria for Adverse Events version 4.0 (CTCAE v 4.0) that is available at <http://ctep.cancer.gov/reporting//ctc.html>.

Adverse events not listed in the NCI Common Terminology Criteria for Adverse Events will be evaluated using the following criteria:

- Grade 1: Mild; asymptomatic or mild symptoms; clinical or diagnostic observations only; intervention not indicated
- Grade 2: Moderate; minimal, local or noninvasive intervention indicated; limiting age-appropriate instrumental ADL
- Grade 3: Severe or medically significant but not immediately life-threatening; hospitalization or prolongation of hospitalization indicated; disabling; limiting self care ADL
- Grade 4: Life-threatening consequences; urgent intervention indicated
- Grade 5: Death related to AE

Information on all adverse events, whether reported by the participant, directly observed, or detected by physical examination, laboratory test or other means, will be collected, recorded, followed and reported as described in the following sections.

Participants should be instructed to report any serious post-study event(s) that might reasonably be related to participation in this study. The investigator should notify the IRB and any other applicable regulatory agency of any unanticipated death or adverse event occurring after a participant has discontinued or terminated study participation that may reasonably be related to the study.

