11.6 Intensity Modulated Radiation Therapy

All radiation related adverse events will be recorded on the local toxicity case report forms. Neoadjuvant intensity modulated radiation therapy (IMRT) and capecitabine chemotherapy is considered standard of care treatment for localized rectal cancer.

In accordance RTOG 0822, “side effects expected from radiation therapy include fatigue, rectal frequency, diarrhea, urinary frequency, dysuria, loss of pubic hair, hyperpigmentation of the skin in the treatment field, lower blood counts. Rare but possible side effects include small bowel obstruction, fistula, small bowel ulceration, wet desquamation, infection, and urethral obstruction.”

The following are common potential short term reactions/ risks that are associated with external beam radiation therapy:

Increased urinary frequency, urgency, pain, mild to moderate increase in frequency and looseness of bowel movements, fatigue, diarrhea, decreased blood cell count, temporary hair loss in area treated, skin redness and irritation in area treated, vaginal inflammation and bladder inflammation.

The following are uncommon potential short term reactions/ risks associated with external beam radiation therapy:

Nausea or vomiting, darkened skin and dryness in area treated, blood in the urine or stool, nausea or vomiting, painful bowel movements, hemorrhoidal bleeding, increased flatulence (gas), urine or stool leakage, severe difficulty with urination or bowel movements requiring a treatment break, such as for an obstruction requiring surgery.

The following are common potential long term reactions/ risks associated with external beam radiation therapy:

Increased tendency to develop flatulence or diarrhea, more frequent urination and the urine cannot be held as long as normal, impotence or sterility/infertility, temporary bleeding in the gastrointestinal tract or genitourinary tract (bladder, prostate, urethra), subsequent surgery in the treated area may be more difficult, early menopause/sterility, and decreased vaginal secretions.

The following are uncommon long term reactions/ risks associated with external beam radiation therapy:

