11.12 Reporting Procedures

11.12.1 General

Adverse events will be recorded at each visit. If an adverse event requiring medical attention occurs between visits, this will be recorded as well. The variables to be recorded for each adverse event include, but are not limited to, onset, resolution, intensity, action taken, outcome, causality rating and whether or not it constitutes an SAE. The intensity of the adverse event should be captured using CTCAE criteria, version 4.0, when possible.

Pregnancy should be excluded before enrollment. Pregnancy in itself is not reported as an AE unless there is a suspicion that an investigational product may have interfered with the effectiveness of a contraceptive medication.

All adverse events will be captured on the appropriate study-specific case report forms (CRFs).

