14. STATISTICAL CONSIDERATIONS

14.1 Endpoints

14.1.1 Study Design

This is a multi-institutional, randomized, two-arm, phase II trial of endorectal brachytherapy alone (Endo-HDR) versus intensity modulated external beam radiotherapy (IMRT) or 3-D conformal radiation therapy with capecitabine in patients with stage II/III rectal distal adenocarcinoma. Patients enrolled in the study will be randomized (2:1 ratio) to either Endo-HDR or standard external beam chemoradiation.

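### Section 11.8 records chemotherapy effects only at grade 3 or higher, against 11.12.1; followed for capecitabine, it drops low-grade events from the control arm alone

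*Combined protocol and SAP*

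**What the plan says.** All references are to the combined protocol and SAP.

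- **11.8 Chemotherapy:** "Only grade 3 or greater side effects thought to be related to chemotherapy will be recorded". The reason given is that chemotherapy is standard of care, and adjustments to the regimen are left to the treating oncologists. The side-effect lists that follow name capecitabine only.
- **11.12.1 General:** "All adverse events will be captured on the appropriate study-specific case report forms (CRFs". There is no grade limit and no exception for chemotherapy.
- **11.6 Intensity Modulated Radiation Therapy:** "All radiation related adverse events will be recorded on the local toxicity case report forms". Again there is no grade limit.
- **11.1 General:** information on all adverse events "will be collected, recorded, followed and reported as described in the following sections". This defers to later sections, so 11.8 can be read as an exception to it. I do not count it as a conflict.
- **14.1.1 Study Design:** the comparison is "endorectal brachytherapy alone (Endo-HDR) versus intensity modulated external beam radiotherapy (IMRT) or 3-D conformal radiation therapy with capecitabine".
- **14.5 Analysis of Secondary Endpoints:** acute and chronic toxicity is tabulated by type and grade for each arm, and the arms are compared with Fisher's exact tests. Section 4.2 makes this comparison a secondary objective.
- **Section 9, calendar footnote 12:** adjuvant chemotherapy is neither monitored nor tracked by the study team.

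**The concern.** A recording floor that applies to one class of attributed events does no harm to a comparison if both arms can have such events. Here they cannot. Before surgery an Endo-HDR patient receives no chemotherapy, so no event in that arm can be attributed to it. Followed for capecitabine, the floor can remove events only from the control arm, and only at grades 1-2.

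The 14.5 tables would then set a complete low-grade count for Endo-HDR beside an incomplete one for control. The direction is to understate low-grade control toxicity. That works against the hypothesis in section 1 of lower toxicity with Endo-HDR, and could hide part of a real advantage.

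**Working it through.** The plan states no figure on this point, so there is none to reproduce. The check is a comparison of texts, followed by illustrations of scale.

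**1. Which events are exposed?** Compare the lists in 11.6 (radiation effects, recorded at all grades) and 11.8 (capecitabine effects, grade 3 or higher).

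| Event | In 11.6 | In 11.8 |
|---|---|---|
| Hand-and-foot syndrome | no | yes |
| Mouth sores | no | yes |
| Loss of appetite | no | yes |
| Fatigue | yes | yes |
| Lower blood counts | yes | yes (anemia, neutropenia) |
| Diarrhea | yes | no |
| Skin irritation | yes | no |

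The first three have no route into the record at grade 1-2 if 11.8 governs. The last four have one through 11.6. They are lost only when a case is attributed to chemotherapy and not to radiation.

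**2. Hand-and-foot syndrome.** Under the floor the grade 1-2 row is 0 of 92 versus 0 of 46, whatever happened. Section 11.8 places the effect in its band of more than 50 in 100 people and gives no grade. Taking 50%, with assumed grade 1-2 shares of 25%, 50% and 90%, the missing control patients number:

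- 46 × 0.50 × 0.25 = 5.75
- 46 × 0.50 × 0.50 = 11.5
- 46 × 0.50 × 0.90 = 20.7

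For reference, assuming none of 92 in Endo-HDR, two-sided Fisher p-values are 0.035 for 3 of 46 and 0.0035 for 5 of 46. A handful of recorded cases would show a difference that the floor erases.

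**3. Shared events.** Inputs: 92 and 46 patients (14.2.1); two-sided Fisher's exact test; level 0.05 (assumed, since 14.5 gives none for toxicity); r = share of control events recorded (assumed). The recorded control rate is r × true control rate. The probability of rejection is the sum of the two binomial probabilities over all tables with p ≤ 0.05.

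| True rates, Endo-HDR vs control | r = 1 | r = 0.95 | r = 0.90 |
|---|---|---|---|
| 20% vs 40% (power) | 65% | 57% | 47% |
| 20% vs 20% (false difference) | 3.8% | 3.9% | 4.4% |
| 50% vs 50% (false difference) | 4.7% | 5.5% | 8.0% |

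In the first row the recorded control rates are 40%, 38% and 36%.

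**4. Are the low-grade events seen at all?** Yes. Section 7.3.5 acts on grade 2 hand-foot reaction by number of appearances ("For the first appearance resume at 100% of the dose") and does the same for grade 2 diarrhea. Sites must therefore already grade events that 11.8 would leave off the CRF.

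**The case against.** **11.8 may not concern capecitabine.** Its sentence leaving adjustments to the treating oncologists fits the discretionary adjuvant regimen in 7.4.7 better than capecitabine, whose modifications 7.3.5 sets out. On that reading the preoperative loss disappears. This stands as a real uncertainty. But the only effects listed in 11.8 are those of capecitabine, and a rule for adjuvant treatment alone would conflict with footnote 12 as well as with 11.12.1. Either reading needs a correction.

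**The conflict and the loss cannot both occur.** If 11.12.1 governs, nothing is lost; if 11.8 is a specific exception, there is no contradiction. That is fair as logic. The text does not say which applies, so sites could follow either, and one of the two choices loses data in one arm.

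**Shared events are mostly safe.** This largely stands. Section 7.5.2 says "Diarrhea, skin irritation, fatigue, urinary tract irritation, and decreased blood counts are the main side effects experienced during concurrent chemotherapy" and pelvic radiation, and a reader might infer that every such event is either kept under 11.6 or dropped under 11.8, with a large share dropped. Recorded shares of 75% or 50% would indeed cut power for 20% versus 40% to 22% or 4%, and raise the false-difference rate at equal 50% rates to 27% or 80%. The documents do not support those shares. Section 11.6 names these events itself, and the attribution scale in 11.2.4 is not exclusive: an event can be possibly related to one treatment even when another could readily have produced it.

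**A test on hand-and-foot syndrome settles little,** because Endo-HDR patients get no capecitabine before surgery. This also stands in part: the loss there is mainly descriptive. It is still a loss from a table that is meant to show what each arm endured.

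**Conclusion.** The point holds, conditionally. Section 11.8 states a recording rule that conflicts with 11.12.1. If it is followed for capecitabine, it understates low-grade toxicity in the control arm alone in the 14.5 comparison.

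The loss is certain in kind for effects in 11.8 that 11.6 does not list. For shared events its size is unknown and may be small; the 90-95% figures above are illustrations, not estimates. The event rates, grade splits, recorded shares and 0.05 level are all assumptions. Only the arm sizes and the 50-in-100 band come from the documents.

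Comparisons at grade 3 or higher and the primary pCR analysis are unaffected. The documents do not show that data were in fact lost, since they do not settle which rule sites follow. The correction should be made, because a named secondary objective is exposed and the change is cheap.

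**What to change.** - In 11.8, state that from the start of radiation to surgery adverse events of all grades are recorded in both arms, regardless of attribution.
- Limit the grade 3 rule to postoperative chemotherapy, and write that exception into 11.12.1.
- Reconcile it with calendar footnote 12: either grade 3 or higher events on adjuvant chemotherapy are collected, or they are not.
- For patients already treated, add grade 1-2 events as far as source notes allow. Where they do not, limit the between-arm test for capecitabine-attributable event types to grade 3 or higher.

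The cost is protocol wording and more CRF entries for about 46 control patients. Part of the grading is already done for 7.3.5, and no visits are added. Retrospective completion will be uneven and should be reported as such.

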11.9 Risks of Blood Draws

About 8ml (1 ½ teaspoons) of blood may be drawn before radiation, after radiation, before surgery, and during follow-up for research purposes. Whenever possible, these samples will be obtained at the same time as other routine laboratory studies. Although trained phlebotomists will be obtaining the blood samples, there are minimal risks associated with this procedure. Taking blood may cause some discomfort, bleeding, or bruising where the needle enters the body, and there is a small risk of infection. In rare cases, blood drawing may result in fainting.

11.10 Risks of Radiographic Imaging

Imaging studies (MRI, FDG-PET/CT) are part of standard clinical care. Patients will be given a clinical consent form for each imaging procedure that explains the risks of the procedures.

11.11 Risks of completing the study questionnaires

Patients may get tired or bored when they answering questions or completing questionnaires.

11.12 Reporting Procedures

11.12.1 General

Adverse events will be recorded at each visit. If an adverse event requiring medical attention occurs between visits, this will be recorded as well. The variables to be recorded for each adverse event include, but are not limited to, onset, resolution, intensity, action taken, outcome, causality rating and whether or not it constitutes an SAE. The intensity of the adverse event should be captured using CTCAE criteria, version 4.0, when possible.

Pregnancy should be excluded before enrollment. Pregnancy in itself is not reported as an AE unless there is a suspicion that an investigational product may have interfered with the effectiveness of a contraceptive medication.

All adverse events will be captured on the appropriate study-specific case report forms (CRFs).

11.12.2 Institutional Review Board

All adverse events and serious adverse events will be reported to the IRB per current institutional standards. If an adverse event requires modification of the informed consent, these modifications will be provided to the IRB with the report of the adverse event. If an adverse event requires modification to the study protocol, these modifications will be provided to the IRB as soon as is possible.

11.12.3 SAE Guidelines for Johns Hopkins Hospital

All SAEs, with the exception of death, must be reported to the Johns Hopkins Medicine Institutional Review Board (JHM-IRB) within 10 working days of the Principal Investigator learning of the event. Reporting for the death of a patient which was unexpected (i.e.: not related to a risk of participation that was listed in the protocol or the consent document, and was more likely than not to be caused by the research procedure/intervention) must be reported to the JHM-IRB within 3 working days of when the Principal Investigator receives the report of the death. Reporting for death of a participant that was expected due to the nature of the patient's underlying disease or condition, or identified as caused by a possible risk of the study procedure/intervention as described in this protocol or consent form, must be reported to the JHM-IRB within 10 working days from the time the Principal Investigator learns of the event. If death occurs 30 days after the participant has stopped or completed their study treatment, the Principal Investigator does not have to report the death until the time of continuing review.

12. DATA AND SAFETY MONITORING PLAN

This is a DSMP Level I study under the SKCCC Monitoring Plan (see Appendix I). A Level I study requires both internal and external data monitoring. The Principal Investigator is responsible for internal monitoring for both safety and data quality. External data monitoring will be performed by the SKCCC at Johns Hopkins Clinical Research Office Quality Assurance Program (CRO QA).

Data and safety monitoring oversight will be conducted by the SKCCC at Johns Hopkins Safety Monitoring Committee. Per the SKCCC at Johns Hopkins Safety Monitoring plan, the CRO QA will forward summaries of all monitoring reports to the Safety Monitoring Committee for review. All reportable anticipated and unanticipated protocol events/problems and amendments that are submitted to the IRB will also be reviewed by the Safety Monitoring Committee Chair (or designee) and QA manager.

12.1 Data Recording

Data will be collected on Case Report Forms (CRFs). These CRFs will be completed by the Study Coordinator. The CRFs for each subject will be kept in a separate research binder. Along with each completed CRF there will be corresponding source documentation filed for verification. The Principal Investigator, Research Study Nurse, and Study Coordinator will informally meet on a regular basis to make sure that the trial is progressing as mandated by the protocol. The CRO will audit this trial per their

standards to ensure and verify that the protocol is being carried out according to specifications as well as to verify that data included on subject CRFs are accurate. Exit reports generated as a result of these CRO audits will be forwarded to both the Safety Monitoring Committee as well as to the IRB of record for review.

13. REGULATORY CONSIDERATIONS

13.1 Protocol Review and Amendments

Information regarding study conduct and progress will be reported to the Institutional Review Board (IRB) per the current institutional standards.

Any changes to the protocol will be made in the form of an amendment and must be approved by the IRB prior to implementation.

